### 9.3.6.2 Information to be Provided by the Investigator

Any SAE for all enrolled subjects must be recorded on the SAE form (during study participation). This requirement includes all SAEs that occur after informed consent and through **28 days after last** dose of study drug, and in addition, any SAEs that are assessed as possibly related to study drug by the Investigator, even if the SAE occurs more than 28 days after the last dose of study drug must be reported to the Kadmon Corporation Pharmacovigilance Department (or designee).

The minimum information required for SAE reporting includes identity of Investigator, site number, subject number, an event description, SAE term(s), onset date, the reason why the event is considered to be serious (i.e., the seriousness criteria) and the Investigator's assessment of the relationship of the event to study drug. Additional SAE information including medications or other therapeutic measures used to treat the event, action taken with the study drug due to the event, and the outcome/resolution of the event will be recorded on the SAE form for reporting which will be provided to the study sites.

In all cases, the Investigator should continue to monitor the clinical situation and report all material facts relating to the progression or outcome of the SAE. Furthermore, the Investigator may be required to provide supplementary information as requested by the Kadmon Corporation Drug Safety personnel or designee.

When reporting SAEs, the following additional points should be noted:

- When the diagnosis of an SAE is known or suspected, the Investigator should report the diagnosis or syndrome as the primary SAE term, rather than as signs or symptoms. Signs and symptoms may then be described in the event description. For example, dyspnea should not be used as an SAE term if the diagnosis which caused the dyspnea is known to be malignant pleural effusion.
- Death should not be reported as an SAE, but as an outcome of a specific SAE, unless the event preceding the death is unknown. In the exceptional case where the events leading to death are unknown, then death may be used as an event term. If an autopsy was performed, the autopsy report should be provided.
- While most hospitalizations necessitate reporting of an SAE, some hospitalizations do not require SAE reporting, as follows:

- Elective or previously scheduled surgery (e.g., a previously scheduled ventral hernia repair)
- Procedures for pre-existing conditions that have not worsened after initiation of treatment
- Pre-specified study hospitalizations for observation
- Events that result in hospital stays of less than 24 hours and that do not require admission (e.g., an emergency room visit for hematuria that results in a diagnosis of cystitis and discharge to home on oral antibiotics)
- SAEs must, however, be reported for any surgical or procedural complication resulting in prolongation of the hospitalization.

### **9.3.6.3 Regulatory Reporting**

Kadmon Corporation Pharmacovigilance Department (or designee) will process and evaluate all SAEs as soon as the reports are received. For each SAE received, Kadmon Corporation will determine whether the criteria for expedited reporting have been met.

Kadmon Corporation (or designee) will submit SAEs that meet the criteria for expedited reporting to the Regulatory Authorities in accordance with local regulations governing safety reporting. Reporting of SAEs by the Investigator to his or her IRB/IEC will be done in accordance with the standard operating procedures and policies of the IRB/IEC. Adequate documentation must be maintained showing that the IRB/IEC was properly notified.

## **9.4 FOLLOW-UP FOR ADVERSE EVENTS**

Any SAE or AE assessed as at least possibly related that led to treatment discontinuation (including clinically significant abnormal laboratory values that meet these criteria) and is ongoing 28 days after last dose of study drug must be followed until either resolution of the event or determination by the Investigator that the event has become stable or irreversible. This follow-up guidance also applies to possibly related SAEs that occur more than 28 days after last dose of study drug. The status of all other continuing AEs will be documented as of 28 days after last dose of study drug.

## **9.5 OTHER SAFETY CONSIDERATIONS**

### **9.5.1 Laboratory Data**

All laboratory data obtained during the course of the study should be reviewed. Any abnormal value that leads to a change in subject management (e.g., dose reduction or delay, requirement for additional medication or monitoring) or is considered to be of clinical significance by the Investigator should be reported as an AE and/or SAE as appropriate, unless this value is consistent with the subject's present disease state or is consistent with values obtained before entry into the study.

Laboratory results will be classified using the CTCAE v5.0.

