## 1. INTRODUCTION

### 1.1 BACKGROUND

Systemic sclerosis, also known as scleroderma, is a chronic autoimmune disease primarily affecting the skin, but with systemic manifestations. Diffuse cutaneous systemic sclerosis is a more serious form of the disease and is often rapidly progressive, involving not only the skin but also internal organs including kidney, heart, and lungs.

The estimated annual incidence of systemic sclerosis in the United States is 20 cases per million with a prevalence of 240 cases per million population. Racial disparities exist and there is an increased incidence and severity in African-Americans. Women are far more likely to acquire the disease and make up 80%-90% of the systemic sclerosis population.

It has been estimated that up to 60% of systemic sclerosis patients will develop interstitial lung disease. This interstitial disease begins with an inflammatory alveolitis suggesting that anti-inflammatory therapy may be of benefit at early stages.

Systemic sclerosis has the highest case-specific mortality among all systemic autoimmune diseases. Pulmonary hypertension, pulmonary fibrosis, and cardiac complications are the most frequent causes of death. The single most common cause of mortality is pulmonary fibrosis from interstitial lung disease.

There remains a substantial unmet medical need for therapies with improved tolerability and effectiveness for patients with systematic sclerosis.

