### **1.3 BELUMOSUDIL NONCLINICAL EXPERIENCE**

In vitro, belumosudil has demonstrated an impact on the T-helper 17 (Th17) and regulatory T cells (Treg)-immune responses as well as on the actin/myosin cytoskeletal network and collagen formation. In vivo, belumosudil has demonstrated efficacy in a variety of clinically relevant animal models of disease including chronic graft versus host disease (cGVHD), scleroderma, idiopathic pulmonary fibrosis (IPF), and other autoimmune diseases.

Good Laboratory Practice (GLP) compliant rat and dog general toxicology/toxicokinetic studies of acute, subchronic (1-and 3-month), and chronic (6-month rat and 9-month dog) duration have been completed. In addition, safety pharmacology (human ether-à-go go related gene [in vitro], central nervous system [rat], respiratory [rat], and cardiovascular [dog]), embryo-fetal toxicology [rat and rabbit], male/female fertility [rat]), genotoxicity, and phototoxicity studies have also been completed. The primary nonclinical toxicology finding at/near clinically relevant exposures were limited to changes in the cardiovascular (blood pressure [BP] lowering), hepatic (transaminitis, hypertrophy/increased organ weight, and

cholestasis/inflammation), renal (increased blood urea nitrogen [BUN], tubular changes, pigmentation, intracellular protein droplets in the epithelium), gastrointestinal (decreased appetite), and hematopoietic/immunologic (anemia with regeneration and thymic/splenic lymphoid depletion) systems.

Belumosudil demonstrated embryo-fetal toxicity/teratogenicity as well as reduced male fertility (reduced fertility index/sperm concentration/motility and increased abnormal sperm percentage), and changes in the testes/epididymis (decreased organ weights and degenerative histopathology). Male fertility findings were generally at higher than clinically relevant exposures.

All pivotal non-clinical safety studies (i.e., those studies identified in International Conference on Harmonisation guidelines as needing to be conducted in accordance with GLP) were conducted in a country that is a member of the Organisation for Economic Cooperation and Development (OECD) Mutual Acceptance of Data program in accordance with the OECD Test Guidelines and Principles of GLP. Study details and potential clinically relevant findings from these studies are summarized in the belumosudil [Investigator's Brochure \(IB\)](#).

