**Table 4 Clinical Laboratory Panels**

Hematology	Serum Chemistry	Other

White blood cell count with differential (including at minimum: neutrophils, basophils, eosinophils, lymphocytes, monocytes)

Red blood cell count

Hemoglobin

Hematocrit

Platelet count

MCV

	

Albumin

Alkaline phosphatase

ALT

AST

BUN

Calcium

Chloride

CO2

Creatinine/GFR

CPK

Total and direct bilirubin

GGT

Globulin

Glucose

HBV (screening only)

HCV (screening only)

HIV (screening only)

Lactate dehydrogenase

Magnesium

Phosphorus

Potassium

Sodium

Total protein

Uric acid

	

Whole blood tuberculin test (screening only)

Urinalysis

Abbreviations: ALT = alanine aminotransferase; AST = aspartate aminotransferase; BUN = blood urea nitrogen, CPK = creatinine phosphokinase; GFR = glomerular filtration rate; GGT = gamma glutamyl transferase; HBV = hepatitis B virus; HCV = hepatitis C virus; HIV = human immunodeficiency virus; MCV = mean corpuscular volume

Abnormalities in clinical laboratory tests that lead to a change in subject management (e.g., dose delay, requirement for additional medication or monitoring) are considered clinically significant for the purposes of this study and will be recorded on the AE eCRF page. Laboratory results will be classified using the CTCAE v5.0. If laboratory values constitute part of an event that meets criteria defining it as serious, the event (and associated laboratory values) must be reported as an SAE (see [Section Error! Reference source not found.](#)).

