## 8. PHARMACODYNAMICS

## 9. SAFETY

### 9.1 SAFETY PARAMETERS

Safety data will be collected from the time the subject signs the ICF form until 28 days after their last dose of study drug (the AE reporting period). The primary safety outcome will be the percentage of subjects experiencing TEAEs and SAEs.

Safety assessments will include AEs, SAEs, PEs, vital sign measurements, clinical laboratory evaluations (hematology, chemistry, and urinalysis), and ECGs. Reasons for treatment discontinuation because of toxicity will be documented.

All AEs that occur in enrolled subjects during the AE reporting period must be recorded regardless of the relationship of the AE to study drug. Any known untoward event that occurs beyond the AE reporting period that the Investigator assesses as possibly related to study drug also should be reported to Kadmon.

Careful monitoring of all toxicities will be carried out. Vital sign measurements, including BP, pulse rate, respiratory rate, and temperature will be monitored throughout the study.

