### 9.2 ADVERSE EVENT DEFINITION

An AE is defined as any untoward medical occurrence in a clinical trial subject associated with the use of a drug, whether or not considered drug related. An AE can be an unfavorable and unintended sign (e.g., an abnormal laboratory value finding), a symptom, or a disease temporally associated with the use of a drug, without judgment as to causality. An AE can arise from use of the drug (e.g., use in combination with another drug) and from any route of administration, formulation or dose, including an overdose. An AE also includes, but is not limited to, any clinically significant worsening of a pre-existing condition. Examples include:

- Any sign, symptom, physical finding, or laboratory result that has worsened in nature, severity or frequency compared to baseline
- Reactions from an investigational drug, including those occurring as a result of an overdose, abuse of the study drug, withdrawal phenomena, sensitivity, or toxicity
- Concurrent illness that was not present or worsens in nature, severity, or frequency compared to baseline
- Injury or accident; and/or

- Exacerbation of a pre-existing condition

For the purpose of data collection, all untoward events that occur after informed consent through 28 days after last dose of study drug are to be recorded on eCRFs by the investigational site.

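### Protocol 9.5.1 exempts from AE reporting some laboratory abnormalities that 6.2.4 and 9.2 treat as AEs, so TEAE counts can depend on which section a site follows, with any error downward

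*Protocol*

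**What the plan says.** Four protocol sections bear on when a laboratory abnormality becomes an AE.

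- **9.5.1 Laboratory Data.** The first trigger is "Any abnormal value that leads to a change in subject management (e.g., dose reduction or delay, requirement for additional medication or monitoring"). The second is a value that the Investigator considers clinically significant. Such values are to be reported as an AE or SAE "unless this value is consistent with the subject's present disease state or is consistent with values obtained before entry into the study". As the sentence is built, the exception applies to both triggers.
- **6.2.4 Clinical Laboratory Parameters** (text under Table 4). Abnormalities that change subject management "are considered clinically significant for the purposes of this study and will be recorded on the AE eCRF page". There is no exception.
- **9.2 Adverse Event Definition.** The examples of an AE include a "laboratory result that has worsened in nature, severity or frequency compared to baseline" and the exacerbation of a condition that was already present. There is no exception for values that fit the disease.
- **9.1 Safety Parameters.** AEs arising in the reporting period "must be recorded regardless of the relationship of the AE to study drug". The same section says: "The primary safety outcome will be the percentage of subjects experiencing TEAEs and SAEs".

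SAP 3.9.1 defines a TEAE as an AE that occurs or worsens after first dosing. It tabulates TEAEs by system organ class and preferred term, and separately those leading to dose modification or interruption. Each of these tables starts from an AE record.

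**The concern.** The two laboratory sections start from nearly the same trigger and reach different answers. Suppose a creatinine rise leads to a pause in dosing and the site attributes it to scleroderma kidney disease. Under 6.2.4 it is an AE. Under 9.5.1 it need not be reported.

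The disease-state part of the exception asks the site to judge cause before deciding whether to record. The protocol already has a place for that judgement, the five-point relationship scale in 9.3.3. Once an event is recorded, a disease explanation is visible and can be reviewed; if it is never recorded, nothing in the AE data shows that a judgement was made. The SAP rule that treats a missing relationship as related (3.1.6) also needs an AE record to act on.

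The study is open-label with a single cohort, so there is no comparator against which to check attribution to disease. Drug and disease can also point to the same organ: the nonclinical findings include "renal (increased blood urea nitrogen [BUN], tubular changes", and the disease is described as "involving not only the skin but also internal organs including kidney, heart, and lungs". At stake is whether TEAE percentages from 12 to 15 subjects at 5 to 6 sites rest on one recording rule.

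**Working it through.** The documents give no figure on this point to reproduce. The check is a comparison of the rules, followed by arithmetic for scale.

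**Step 1. Apply each rule to the same value.**

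| Post-dose laboratory value | 6.2.4 | 9.2 | 9.5.1 |
|---|---|---|---|
| Changed management, worse than baseline, fits the disease | AE | AE | exempt |
| Changed management, worse than baseline, matches an older pre-entry result | AE | AE | exempt |
| Clinically significant, worse than baseline, no management change, fits the disease | silent | AE | exempt |
| Changed management, no worse than baseline | AE | not a worsened result | exempt if it matches pre-entry values |
| No worse than baseline, no management change | silent | not a worsened result | exempt if it matches pre-entry values |

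Rows 1, 2 and 4 contradict 6.2.4. Rows 1 to 3 contradict 9.2. Row 5 is harmless.

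**Step 2. The pre-entry comparator.** SAP 3.1.5 defines baseline as the last valid value within 29 days before first dose. The comparator in 9.5.1 has no time window and is not tied to that baseline. Protocol 3.5 excludes renal crisis only within 4 months before enrollment, so a subject may have older, worse renal values on file. A post-dose value worse than baseline could match one of those and be dropped (row 2).

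**Step 3. Direction.** The exception can only remove AE records, so any effect on TEAE counts is downward. Its size would need the frequency of exempted values and the share of sites following 9.5.1. The documents give neither.

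**Step 4. Scale of one omission.** Change in a subject-level percentage = 100/n, with n from Protocol 9.7.2.

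- n = 12: 100/12 = 8.3 points
- n = 15: 100/15 = 6.7 points

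This holds only if the omitted event is the subject's sole TEAE, or sole one under the term or category tabulated. Otherwise the change is 0.

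**Step 5. Illustration, with assumed counts and exact (Clopper-Pearson) 95% intervals.**

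| n | With the event | With one subject's event omitted |
|---|---|---|
| 12 | 2/12 = 16.7% (2.1 to 48.4) | 1/12 = 8.3% (0.2 to 38.5) |
| 15 | 2/15 = 13.3% (1.7 to 40.5) | 1/15 = 6.7% (0.2 to 31.9) |

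A term-level rate halves, although the intervals are wide in either case.

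**The case against.** The strongest reply is that this is a wording inconsistency in a small exploratory study where safety is a secondary objective, and that little is lost even if a site follows 9.5.1. Much of that is right.

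- **The laboratory data survive.** SAP 3.9.2 provides shift tables to worst grade and a listing of Grade 3 or higher results. Protocol 9.9 summarises the incidence of laboratory abnormalities. Table 2 requires a dedicated form for Grade 3 or higher liver tests. SAP 3.7 tabulates doses held and reduced with reasons, so the dose pause in the example would still appear.
- **SAE reporting.** A reader might infer that 24-hour SAE reporting is lost. The exception is worded for an abnormal value. Seriousness is defined by outcome in 9.3.1, 9.3.6.2 requires any SAE to be recorded, and 6.2.4 requires SAE reporting when laboratory values form part of a serious event.
- **Follow-up.** A reader might infer that extended follow-up under 9.4 is lost. For non-serious events that rule covers AEs at least possibly related that led to treatment discontinuation. A non-serious dose pause attributed to disease falls outside it even when recorded.
- **Target organs.** A reader might infer under-counting across the organs the drug affects. The laboratory overlap between drug and disease that the documents show is renal, and the drug side of it is nonclinical. The clinical signal in 1.4.2 is transaminases, where the exception has little room: liver disease is excluded (3.5), entry limits apply to ALT, AST and bilirubin (3.4), and 1.1 does not name the liver among the organs involved.
- **Section 9.1.** Its rule governs events that are already AEs. The conflict with it is indirect and runs through the definition in 9.2.

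What stands is that none of these back-stops produces a TEAE. Term-level counts, causality tables and the tables of TEAEs leading to dose modification or interruption all need the AE record, and 6.2.4 and 9.5.1 disagree on whether one is made.

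**Conclusion.** The contradiction between 9.5.1 and 6.2.4, and between 9.5.1 and the AE definition in 9.2, is plain on the page and should be resolved. The disease-state part of the exception does most of the harm. The pre-entry part matters for values that changed management and for values worse than study baseline that match an older result.

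The effect on results is less certain. It is downward, it arises only where a site follows 9.5.1 over 6.2.4, and its size cannot be estimated. The range of 6.7 to 8.3 points per omission assumes 12 to 15 subjects and an event that is the subject's only one in the category counted. A reader might apply that range to the overall percentage of subjects with any TEAE. The documents do not support this, because a subject with any other TEAE over 52 weeks leaves that percentage unchanged. The exposure is in specific terms and in TEAEs leading to dose modification or interruption.

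**What to change.** Amend 9.5.1 so that it agrees with 6.2.4 and 9.2:

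- Remove the exception for any abnormality that led to a change in management.
- Remove it for any clinically significant value that is worse than study baseline, whether or not management changed. Dealing with management-changing values alone would leave the conflict with 9.2 in place.
- State that a disease explanation is recorded in the causality assessment and is not a reason to leave the event unrecorded.
- Keep the exception only for values no worse than the baseline defined in SAP 3.1.5 that led to no change in management.

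A memo to the sites should say that this one rule applies to all of them. If subjects have already been treated, sites should review management-changing and worsened, clinically significant laboratory values for events left unrecorded under 9.5.1.

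The change concerns recording only and alters no dosing or stopping rule. It costs a short amendment and the memo. A few more laboratory AEs will be recorded, so TEAE rates will look slightly less favourable.

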### **9.5.2 Medication Errors**

Any medication error that results in an AE, even if it does not meet the definition of serious, requires reporting within 24 hours to the safety monitor.

## **9.6 STUDY STOPPING RULES**

### **9.6.1 Stopping Rules for Study**

Kadmon reserves the right to discontinue the trial at any time for the following reasons:

1. Failure to meet expected enrollment goals
2. Emergence of any safety information that could significantly affect continuation of the trial
3. Violation of GCP (R2), the Clinical Trial Program, or the contract by a trial site or Investigator, or any other administrative reasons, disturbing the appropriate conduct of the trial
4. Results from other competing clinical trials make this trial not worthy to continue

### **9.6.2 Stopping Criteria for Subjects**

Subjects will be discontinued from the study at any time for the following reasons:

1. Grade  $\geq 3$  LFT increase (AST, ALT, or total bilirubin)
2. Grade  $\geq 3$  clinically significant toxicity considered related to belumosudil
3. QTc  $> 500$  ms or AE of *Torsades de pointes*

## 9.7 STATISTICAL CONSIDERATIONS

### 9.7.1 Hypothesis

This study will explore the efficacy of belumosudil 200 mg BID on proposed primary and secondary endpoints. The main focus is to provide guidance for follow-up studies.

### 9.7.2 Sample Size

This is an exploratory study. Sample size and power are not driven by hypothesis testing. Twelve to 15 subjects will be enrolled to receive PO administered belumosudil 200 mg BID.

### 9.7.3 Analysis Populations

Two populations will be employed in the analysis of study data:

- Modified Intent-to-Treat (mITT) Population: All subjects who receive at least 1 dose of belumosudil 200 mg.
- Safety Population: As with the mITT Population, all subjects who received at least 1 dose of belumosudil 200 mg.

Efficacy analyses will be performed on the mITT Population. Safety analyses will be performed on the Safety Population.

